16.4.2 Viral Status

Listing of viral status parameters (HIV, HBV, HCV and HDV) will be provided.

16.4.3 Other Laboratory Parameters

All other parameters collected on the eCRF will be listed in dedicated listings presenting all data collected in the eCRF:

- Basic urinalysis (pH, Specific gravity, Glucose, Bilirubin, Ketones, Blood, Color, Protein, Nitrite, Leukocyte esterase, Urobilinogen, Macroscopic appearance) and Urinalysis microscopic evaluation (Red blood cell count, White blood cell count, Epithelial cells, Bacteria, Crystals, Casts, Mucus)
- Serum electrophoresis (Total protein, Albumin) Only for dose escalation
- Hormonal test (ACTH, ANA, RF, T4, TSH)
- Pregnancy test

Those listings will be sorted by assigned dose level/cohort, subject identifier, lab category, and parameters within each lab category, date.

16.5 Vital Signs

Quantitative data will be summarized all dose level/cohorts combined (where applicable) and by dose level/cohort using simple descriptive statistics (mean, SD, median, Q1, Q3, minimum, and maximum) of actual values and changes from baseline over time.

The maximum changes of vital sign measurements from the baseline to maximum on-treatment change will be grouped as follows:

Table 11 Categories of Maximum Change from Baseline in Vital Signs

Vital Sign Parameter	Increase/ decrease	Baseline category	Change from baseline category
Temperature	Increase	<37 °C, 37 - <38 °C 38 - <39 °C 39 - <40 °C ≥ 40 °C	< 1°C, 1-<2°C, 2-<3°C, ≥ 3 °C
Weight	Increase	Any	<10%, ≥10%
	Decrease	Any	<10%, ≥10%
Heart rate	Increase	<100 beats/min; ≥ 100 beats/min	≤20 beats/min, >20 – 40 beats/min, >40 beats/min
	Decrease	<50 beats/min; ≥ 50 beats/min	≤20 beats/min, >20 – 40 beats/min, >40 beats/min
SBP	Increase	<140 mmHg; ≥ 140 mmHg	≤20 mmHg, >20 – 40 mmHg, >40 mmHg
	Decrease	<95 mmHg; ≥ 95 mmHg,	≤20 mmHg, >20 – 40 mmHg, >40 mmHg
DBP	Increase	<90 mmHg; ≥ 90 mmHg	≤20 mmHg, >20 – 40 mmHg, >40 mmHg
	Decrease	<45 mmHg; ≥ 45 mmHg	≤20 mmHg, >20 – 40 mmHg, >40 mmHg
Respiration rate	Increase	<20 breaths/min;	≤5 breaths/min,

Vital Sign Parameter	Increase/ decrease	Baseline category	Change from baseline category
		≥ 20 breaths/min/min	>5 – 10 breaths/min, >10 breaths/min
	Decrease	<20 breaths/min; ≥ 20 breaths/min	≤5 breaths/min, >5 – 10 breaths/min, >10 breaths/min

For each patient, the worst on-treatment value will be calculated. Missing values will define a separate category.

The following summaries will be prepared for vital sign parameters as grouped above, considering only subjects with post baseline values:

- Maximal Shifts (changes in categories)
- Listing of highest change per subject

A table of potentially clinically meaningful changes will also be displayed:

- \leq 95 mmHg and decrease from baseline \geq 20 mmHg in systolic blood pressure
- \geq 140 mmHg and increase from baseline \geq 20 mmHg in systolic blood pressure
- \leq 45 mmHg and decrease from baseline \geq 20 mmHg in diastolic blood pressure
- \geq 90 mmHg and increase from baseline \geq 20 mmHg in diastolic blood pressure
- \leq 50 beats/min and decrease from baseline \geq 20 beats/min in heart rate
- \geq 100 beats/min and increase from baseline \geq 20 beats/min in heart rate
- $\geq 10\%$ weight increase
- $\geq 10\%$ weight decrease

A listing of vital sings will be provided. The Listing will include assigned dose level/cohort, subject identifier, age, sex, vital sign parameter (units), visit, date, value, baseline value, change from baseline. The listings will be sorted by assigned dose level/cohort, subject identifier, vital sign parameter, and vital sign measurement date.

16.6 Other Safety or Tolerability Evaluations

16.6.1 ECG

The 12-lead Electrocardiogram (ECG) assessments will be performed according to the Schedule of Assessments in the Clinical Trial Protocol.

ECG summaries will include all ECG assessments at baseline and during the on-treatment period. All ECG assessments will be listed, and those collected outside the on-treatment period will be flagged in the listing.

The following analyses will be performed all dose level/cohorts combined (where applicable) and by dose level/cohort, during the on-treatment period.

• Shift table from normal baseline values to abnormal post-baseline values.

A listing of ECG values will be provided. The listing will include dose level/cohort, subject identifier, age, sex, ECG parameter, visit, ECG date, value, unit, baseline value, change from baseline, any abnormal findings. Qualitative ECG results will also be provided in the listing. The listing will be sorted by dose level/cohort, subject identifier, ECG parameter, and ECG date.

16.6.2 ECOG Performance Status

The ECOG shift from baseline to the highest score during the on-treatment period will be summarized for all dose level/cohorts combined (where applicable) and by dose level/cohort. ECOG performance status will also be presented in a listing at each time point.

The outcomes of ECOG Performance Status are defined as below:

- 0: Fully active, able to carry on all pre-disease performance without restriction.
- 1: Restricted in physically strenuous activity but ambulatory and able to carry out work of a light or sedentary nature, e.g., light house work, office work.
- 2: Ambulatory and capable of all selfcare but unable to carry out any work activities. Up and about more than 50% of waking hours.
- 3: Capable of only limited selfcare, confined to bed or chair more than 50% of waking hours.
- 4: Completely disabled. Cannot carry on any selfcare. Totally confined to bed or chair.
- 5: Dead.

16.6.3 Oxygen Saturation

By-visit summaries of oxygen saturation and change from baseline will be provided.

Oxygen saturation will be presented in a listing at each time point with changed values from baseline.

17 Pharmacokinetics and Pharmacodynamics

The analyses described in this section will be performed by the Clinical PK/CCI group (CPK) of Translational Medicine, Merck Healthcare KGaA, Darmstadt, Germany, or by a Contract Research Organization selected by the Sponsor. Pharmacokinetic listings and individual data will be presented based on the SAF. Summaries and statistical analyses will be based on the PKAS.

CCI

Pharmacokinetic concentrations/parameters refer to bintrafusp alfa concentrations/PK parameters. Pharmacodynamic concentrations / PDyn parameters refer to "CD3+ PD-L1 RO%" (also referred to PD-L1 target occupancy), "TGF\u03bb-1", "TGF\u03bb-2", and "TGF\u03bb-3".

17.1 Missing PK/CCI Data

Concentrations below the lower limit of assay quantification

Pharmacokinetic concentrations below the lower limit of quantification (<LLOQ) will be set to zero for calculating parameters and descriptive statistics.

Pharmacokinetic concentrations <LLOQ, which are before the last quantifiable data point, will be taken as zero for calculating the area under the serum concentration-time curve (AUC) of single dose profiles. Concentration below LLOQ, which occur after the last quantifiable data point will not be considered in the calculation of the terminal first order rate constant (λ_z).

Deviations, missing concentrations, and anomalous values

There will be no imputation of missing data. Concentrations will be set to missing in summary tables if the value is reported as no result. Pharmacokinetic/CCI concentrations which are erroneous due to a protocol violation (as defined in the clinical study protocol), documented handling error, or analytical error (as documented in the bioanalytical report) may be excluded from the PK/CCI analysis if agreed upon prior to performing a statistical analysis. In this case the rationale for exclusion must be provided in the relevant listing/table.

Exclusions for concentration data descriptive statistics

- Positive pre-dose values on Day 1
- Concentration observed at the end of infusion (C_{EOI}) < LLOQ
- In case of missed dose, exclude all concentrations until intended dosing is resumed Concentration observed at the end of the dosing interval (C_{trough}) values in case samples are taken at least 7 days late or early

Exclusions for Non-Compartmental Analysis (NCA)

- Positive pre-dose values on Day 1
- C_{EOI} < LLOQ
- In case of missed dose, exclude all concentrations until intended dosing is resumed

Any other PK/CCI concentrations that appear implausible to the Pharmacokineticist/PK/CCI Data Analyst must not be excluded from the analysis. Any implausible data will be documented in the relevant listing/table.

If a PK parameter cannot be derived from a participant's concentration data, the parameter will be coded as NC (not calculated). (Note that NC values will not be generated beyond the day that a participant discontinues the treatment). For statistical analyses, PK parameters coded as NC will be set to missing.

If an individual participant has a known biased estimate of a PK parameter (due for example to a deviation from the assigned dose level), this participant/value will be excluded from the descriptive statistics, and instead the result will be listed in a separate table.

17.2 Descriptive PK and CC Analysis

Presentation of PK/PD Concentration Data

A by-participant listing will present PK concentrations sample times, time deviations, and concentrations based on the SAF. Concentrations will be reported with the same precision as the source data.

Tables

Additional table(s) will summarize PK concentrations with further stratification by ADA subsets ever positive and never positive, based on the PKADA. Additional table(s) will summarize PK concentrations with further sub-stratification by nAb subsets ever positive and never positive, based on the PKNAB. For nAb subsets, summaries will be done for ever positive in either of 2 nAb assays (PD-L1 and TGFß receptor neutralization; see Section 15). Additional table(s) will summarize PK concentrations with stratification by Japanese, andnon-Japanese as applicable, based on the PKAS.

Descriptive statistics of PK/CCI concentration data will be calculated using values with the same precision as the source data and rounded for reporting purposes only. The following conventions will be applied when reporting descriptive statistics of PK/CCI concentration data:

Mean, Min, Median, Max, Q1, Q3, GeoMean:

3 significant digits

StD, logStD: 4 significant digits

CV%, GeoCV%:

1 decimal place

Figures

Individual PK concentration-time profiles showing all participants by treatment and cohort will be created using the actual time points and the numeric concentration data. Plots of individual data will be based on the SAF. Median, GeoMean and Mean concentration-time profiles by treatment and cohort will be provided using scheduled (nominal) time points and the numeric concentration data. All concentration-time plots for PK data will be presented both on a linear and on a semi-logarithmic scale.

Mean and GeoMean PK plots will include StD or logStD error bars when plotted on a linear scale. Summary (Mean/Median) PK plots will be based on the PKAS.

Additional figures will present Mean, GeoMean, and Median PK concentration-time profiles with further stratification by ADA subsets ever positive and never positive, based on the PKADA. Additional figures will present Mean, GeoMean and Median PK concentration-time profiles with further sub-stratification by nAb subsets ever positive and never positive (see Section 15), based on the PKNAB. Additional figures will present Mean and Median PK concentration-time profiles with stratification by Japanese and non-Japanese as applicable, based on the PKAS.

CC

A line

displaying the LLOQ of the corresponding assay will be added. Plots will be presented on a linear scale only, and data will be based on the SAF.

CCI

A line displaying the LLOQ of the corresponding assay will be added. Data will be based on the PKAS.

Pharmacodynamic metrics ("TGFß" concentrations) will be plotted against PK concentrations (bintrafusp alfa), for all participants both on a linear and on a semi-logarithmic scale. Only PK samples, both taken at the same time points following intravenous (IV) infusion on Day 1 are part of these plots. These plots will be based on the PKAS.

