The dose escalation part will use a standard 3+3 scheme with the planned doses of 3 mg/kg, 10 mg/kg, and 20 mg/kg administered once every 2 weeks. For each dose level, DLTs are assessed during the first 3 weeks (21 days after administration of MSB0011359C). The criteria for moving from one dose level to another do not allow escalation to the next cohort in cases where more than 1 subject in a cohort experiences a DLT. If 1 of 3 subjects in a cohort experiences a DLT, this cohort will be automatically expanded to 6 subjects. The MTD is defined as the highest dose where no more than 1 subject out of 6 subjects experiences a DLT. Thus, the MTD cohort should accrue at a total of 6 subjects. After the cohort with the dose selected for the expansion part has completed the DLT evaluation period, an additional 3 subjects may be enrolled if a total of 6 subjects have not yet been treated at the dose level for the purpose of additional safety evaluation.

A DLT is defined as any Grade \geq 3 adverse event (AE) (with certain exceptions as described in the protocol) suspected to be related to MSB0011359C by the Investigator and/or Sponsor occurring during the DLT evaluation period (defined as 21 days after administration of MSB0011359C) and confirmed by the Safety Monitoring Committee (SMC) to be relevant for the IMP treatment.

At each dose level, subjects will receive MSB0011359C as a 1-hour intravenous infusion once every 2 weeks until progressive disease (PD) has been confirmed by a subsequent scan, unacceptable toxicity, or occurrence of any criterion for withdrawal from the trial or the IMP as outlined in this protocol. In order to mitigate potential infusion-related reactions, premedication with an antihistamine and with paracetamol (acetaminophen) (eg, 25 to 50 mg diphenhydramine and 500 to 650 mg paracetamol [acetaminophen] intravenous or oral equivalent) approximately 30 to 60 minutes prior to each dose of MSB0011359C is mandatory for the first 2 infusions. Premedication is optional and at the discretion of the Investigator after the second infusion. If Grade 2 infusion reactions are seen during the first two infusions, then premedication should not be stopped. Steroids as premedication are not permitted.

Expansion (Part B):

Document No.

Object No.

The expansion part consists of an HCC cohort and other cohort indications including GC, ESCC, and BTC.

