GeoMean Geometric Mean HBV Hepatitis B Virus

HCC Hepatocellular carcinoma

HCV Hepatitis C virus
HDV Hepatitis D virus

HGB Hemoglobin

HIV Human Immunodeficiency Virus

IAP Integrated Analysis Plan ICF Informed Consent Form

ICH International Council for Harmonization

IMP Investigational Medicinal Product irAE Immune-Related Adverse Event

IRC Independent Review Committee

IRR Infusion-Related Reaction

irTEAE Immune-related Treatment-Emergent Adverse Event

LDH Lactate dehydrogenase

LLN Lower Limit of Normal

LLQ/LLOQ Lower Limit of Quantification

logStD Standard deviation of log-transformed data

Max Maximum

MCH Mean corpuscular hemoglobin

MCHC Mean corpuscular hemoglobin concentration

MCV Mean Corpuscular Volume

Mean Arithmetic Mean

MedDRA Medical Dictionary For Regulatory Activities

Min Minimum

MSI Microsatellite Instability

MSI-H Microsatellite Instability-high

MSS Microsatellite Stable

n Number of non-missing values

NA Not Applicable

nAb Neutralizing Antibody

NC Not calculated

NCA Non-compartmental Analysis

NCI-CTCAE National Cancer Institute – Common Terminology Criteria for

Adverse Events

OR Objective Response

ORR Objective Response Rate

OS Overall Survival

PD Progressive Disease

PD-L1 Programmed death ligand 1

CCI

PFS Progression Free Survival

PK Pharmacokinetic

PKADA Pharmacokinetic ADA Analysis Set

PKAS PK Analysis Set

PKNAB Pharmacokinetic nAb Analysis Set

PR Partial Response

PT Prothrombin Time/Preferred Term

Q1 First Quartile
Q3 Third Quartile
RBC Red Blood Cell

RDI Relative Dose Intensity

RECIST Response Evaluation Criteria in Solid Tumors

RF Rheumatoid Factor
RNA Ribonucleic Acid

RR RR interval

SAE Serious Adverse Event SAF Safety Analysis Set

SBP Systolic Blood Pressure

SD Stable Disease

SDTM Study Data Tabulation Model

SOC System Organ Class StD Standard Deviation $t_{1/2}$ Terminal Half-Life

T4 Thyroxine

TBILI Total Bilirubin
TC Tumor Cells

TEAE Treatment-Emergent Adverse Event TGF β Transforming Growth Factor-Beta t_{max} Time to Maximum Concentration

TME Tumor Microenvironment

TSH Thyroid-stimulating hormone

ULN Upper Limit of Normal

WBC White Blood Cells

WHO-DD WHO Drug Dictionary

WTU Whole tumor

λz Terminal Phase Rate Constant

Modification History

Unique Identifier for Version	Date of IAP Version	Author	Changes from the Previous Version
1.0	29SEP2020	PPD	NA

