The analysis of dose proportionality of PK parameters of M7824 will be quantified as part of an exploratory analysis using the power model on the parameters (ln[PKparameter]= $\alpha + \beta x$ ln[dose]) (mg/kg dosing only, e.g., dose escalation and HCC). This analysis will be based on AUC_{0-\infty}, AUC₀₋₁, AUC₀₋₃₃₆, and C_{max}. The intercept α and the slope β together with 90% CIs will be estimated and presented. A p-value testing whether $\beta = 1$ will also be presented.

Presentation of PK Parameter Data

Individual PK parameters will be listed by nominal study day based on the SAF. Individual PK parameters will be reported with the same precision as the source data.

Pharmacokinetic parameters will be reported to 3 significant figures. In export datasets, as well as in the SDTM PP/XD domain, PK parameters will be provided with full precision and will not be rounded. Descriptive statistics of PK parameter data will be calculated using full precision values and rounded for reporting purposes only.

Pharmacokinetic parameter data will be listed in tables and descriptively summarized by treatment (dose, e.g. 1200 mg) and cohort separately, and day using: n, Mean, StD, CV%, Min, Median, Max, GeoMean, logStD, GeoCV%, and the 95% CI for the GeoMean (LCI 95% GM, UCI 95% GM). Summaries will be based on the PKAS.

Additional table(s) will summarize NCA parameters following first infusion, C_{trough} and C_{EOI} with further stratification by ADA subsets ever positive and never positive, based on the PKADA. Additional table(s) will summarize NCA parameters following first infusion, C_{trough}

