Arithmetic mean $C_{trough} \pm StD$ and $C_{EOI} \pm StD$ and GeoMean $C_{trough} \pm logStD$ and $C_{EOI} \pm logStD$ will be plotted versus nominal day on a linear scale. Median C_{trough} and C_{EOI} will also be plotted versus nominal day on a linear scale. Summary plots will be based on the PKAS. Additional figures will present Mean, GeoMean, and Median C_{trough} and C_{EOI} with further stratification by ADA subsets ever positive and never positive, based on the PKADA. Additional figures will present Mean, GeoMean and Median C_{trough} and C_{EOI} with further sub-stratification by nAb subsets ever positive and never positive, based on the PKNAB. For nAb subsets, summaries will be done for ever positive in either of 2 nAb assays versus never positive (see Section 15). Additional figures will present Mean, GeoMean and Median C_{trough} and C_{EOI} with stratification by Japanese and non-Japanese, based on the PKAS.

For ADA treatment-emergent subjects with at least one C_{trough} measurement before and after ADA seroconversion, individual C_{trough} will be plotted versus PK day relative to seroconversion for each cohort (for readability, split further into groups of 10 subjects or fewer as needed). Box plots will be prepared for C_{trough} versus PK day relative to seroconversion.

For nAb treatment-emergent subjects with at least one Ctrough measurement before and after nAb seroconversion (earliest of 2 assays if positive in both), individual C_{trough} will be plotted versus PK day relative to seroconversion for each cohort (for readability, split further into groups of 10 subjects or fewer as needed). Box plots will be prepared for C_{trough} versus PK day relative to seroconversion.

All above will be summarized by treatment (dose, e.g. 1200 mg across cohorts) and cohort separately.

Dose proportionality will be evaluated for using data from participants with a full PK profile, and will be presented graphically as follows:

Regression plots for individual AUC_{0-t}, AUC₀₋₃₃₆, AUC_{0-∞} and C_{max} values (where applicable) and dose normalized AUC_{0-t}, AUC₀₋₃₃₆, AUC_{0-∞} and C_{max} versus dose on a linear scale. All the above dose proportionality plots will be repeated with further substratification by Japanese and non-Japanese as applicable. Additional plots showing fit of power model described above will be presented for AUC₀-t and Cmax. These plots will be based on the PKAS.

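### As written, the error bars on the geometric-mean PK figures add a log-scale SD to a concentration, so they are invalid and change with the reporting unit

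*SAP*

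**What the plan says.** The abbreviation list (SAP Section 2) gives the definition: "logStD Standard deviation of log-transformed data". It names no log base.

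SAP 17.2 (Figures) describes the summary profiles: "Median, GeoMean and Mean concentration-time profiles by treatment and cohort will be provided using scheduled (nominal) time points and the numeric concentration data". The values plotted are therefore concentrations, not their logs. On axes it says: "All concentration-time plots for PK data will be presented both on a linear and on a semi-logarithmic scale". On bars it says: "Mean and GeoMean PK plots will include StD or logStD error bars when plotted on a linear scale". No bars are specified for the semi-logarithmic versions.

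SAP 17.3 gives the additive form explicitly for the trough and end-of-infusion plots: "GeoMean $C_{trough} \pm logStD$ and $C_{EOI} \pm logStD$ will be plotted versus nominal day on a linear scale". The same sentence treats arithmetic mean ± StD in the same way.

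Both sections then call for further figures by subgroup. Geometric means appear in the ADA and nAb concentration-time figures (17.2) and in the ADA, nAb and Japanese/non-Japanese C_trough and C_EOI figures (17.3). The Japanese/non-Japanese concentration-time figures in 17.2 show the mean and median only. Neither section repeats an error-bar rule for the subgroup figures.

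**The concern.** The SD of logged values describes multiplicative spread. It is a pure number, and it becomes a band around a geometric mean only after exponentiation. Added to a concentration, it gives a bar whose relative size is set by the choice of unit and not by the data. Nothing in the SAP mentions exponentiating it or drawing a multiplicative band.

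At stake is how the figures are read. SAP 15.5 evaluates the effect of ADA on PK descriptively, and SAP Section 4 allows the analyses to go into regulatory submissions or manuscripts, where a figure may be seen without its table. Bars that are far too short make ordinary between-subject spread look like clear separation of curves. Bars that are far too wide, or that fall below zero, hide real differences.

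**Working it through.** The plan gives no figure to reproduce, so the check compares the bar as written with the back-transformed bar.

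**Inputs.** The definition of logStD and the additive rule come from SAP Section 2, 17.2 and 17.3. The documents give neither concentrations nor their unit, so two ranges are assumed: geometric mean G from 0.1 to 400 reporting units, and logStD s from 0.2 to 0.8 on the natural-log scale. Using GeoCV% = 100 × √(exp(s²) − 1), that range of s corresponds to a GeoCV of 20.2% to 94.7%.

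**Formulas.**
- As written: G − s to G + s, width 2s.
- Back-transformed: G × exp(−s) to G × exp(+s), width G × (exp(s) − exp(−s)).
- Width ratio, written over correct: 2s / [G × (exp(s) − exp(−s))]. The part without G is 0.99 at s = 0.2 and 0.90 at s = 0.8, so the ratio is 0.90 to 0.99 divided by G.

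**Results.**

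| G | As written, s = 0.3 | Back-transformed, s = 0.3 | Width ratio, s = 0.2 to 0.8 |
|---|---|---|---|
| 0.1 | −0.2 to 0.4 | 0.074 to 0.135 | 9.0 to 9.9 times too wide |
| 1 | 0.7 to 1.3 | 0.74 to 1.35 | 90% to 99% |
| 5 | 4.7 to 5.3 | 3.7 to 6.7 | 18% to 20% |
| 10 | 9.7 to 10.3 | 7.4 to 13.5 | 9% to 10% |
| 50 | 49.7 to 50.3 | 37.0 to 67.5 | about 2% |
| 100 | 99.7 to 100.3 | 74.1 to 135.0 | about 1% |
| 400 | 399.7 to 400.3 | 296.3 to 539.9 | about 0.2% |

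The lower end as written is negative whenever s exceeds G. At G = 0.1 that means any logStD above 0.1.

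**Unit dependence.** Take s = 0.3. A geometric mean of 100 µg/mL gets a bar of 0.3/100 = 0.3% of the mean. The same value written as 0.1 mg/mL gets 0.3/0.1 = 300%. The back-transformed bar runs from 74% to 135% of the geometric mean in either unit.

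**The case against.** The best defence is that the 17.2 sentence contains no plus-or-minus sign. It could simply name the dispersion statistic and leave the programmer to back-transform, and an experienced programmer may have done so. That is possible for 17.2, but 17.3 does print the sign, on a linear axis, in parallel with arithmetic mean ± StD, and no text says otherwise.

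Three stronger readings are tempting, and the documents do not support them.

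- **Between-subject variability practically disappears from these figures.** That holds only if the geometric means are numerically well above 1 in the reporting unit. Near 1 the bars are about right, and below 1 the error reverses. The documents do not say which case applies.
- **All the ADA, nAb and ethnicity comparisons carry the wrong bars.** The explicit additive form belongs to the unstratified C_trough and C_EOI plots, so extending it to the subgroup figures is an inference. Even then, the Japanese/non-Japanese concentration-time figures are untouched, because they contain no geometric mean.
- **These plots are the plan's means of comparing exposure, so a false conclusion about ADA or ethnicity would follow.** The plan also tabulates concentrations and PK parameters by ADA, nAb and Japanese/non-Japanese status. For PK parameters, 17.3 lists "GeoMean, logStD, GeoCV%, and the 95% CI for the GeoMean" among the summary statistics. It also plans arithmetic mean ± StD plots, and box plots of C_trough by day relative to seroconversion. SAP 9.10 rules out testing of the study endpoints, and the exploratory dose-proportionality model does not use the bars.

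Timing also counts against urgency. This SAP version is dated 11 April 2022, after the CSR addendum was approved on 25 March 2021, and no final analysis will follow. Rewording cannot change figures already delivered. It matters only for reuse.

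**Conclusion.** Wrong as written. The additive rule in 17.3, and in 17.2 read in the same way, puts a unitless log-scale SD on a concentration axis. That is invalid whatever the concentrations turn out to be.

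The size and direction rest on the assumed ranges and natural logs. The error is serious for geometric means of about 10 or more (a tenth of the correct width or less) and for those around 0.1 (9-10 times too wide), and slight near 1. If the same bars are carried to the subgroup figures, it reaches the ADA and nAb concentration-time and C_trough/C_EOI plots and the Japanese/non-Japanese C_trough/C_EOI plots. It is a defect of figures only. No estimate, table, test or decision changes.

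**What to change.** In SAP 17.2 and 17.3, state that error bars on every geometric-mean figure run from GeoMean × exp(−logStD) to GeoMean × exp(+logStD), with logStD calculated on natural logs. Say whether the subgroup figures carry the same bars. Keep arithmetic mean ± StD as it is.

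Before any delivered geometric-mean figure is reused in a submission or manuscript, check how its bars were drawn and reissue it if they were additive.

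The cost is a sentence in each section, a small change to the plotting code if it follows the text, and a check of existing figures. No data, analysis set or tabulated result is affected.
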